6.6 Criteria for Blinatumomab Discontinuation

Treatment with blinatumomab should be discontinued in the event of any of the following:

- Hematological or extramedullary relapse subsequent to achieving $\leq 5\%$ BM blasts on protocol treatment
 - Exception: subjects who develop isolated CNS leukemia, relapse during treatment and who have not met the criteria for an event as defined above, may continue on study and receive additional CNS directed therapy in addition to their systemic protocol-specified therapy. Subjects should receive intrathecal chemotherapy until negative for CNS leukemia before starting blinatumomab.
- Failure to achieve BM response defined as $\leq 5\%$ blasts within 2 treatment cycles
- Occurrence of an adverse event which makes discontinuation from treatment necessary due to protocol specified safety criteria or desirable in the investigator's and/or the subject's opinion
- An infusion interruption of more than 2 weeks due to an adverse event related to blinatumomab (exception: in case of logistical difficulties, restart of treatment can be postponed for up to 7 additional days without resulting in permanent treatment discontinuation)
- Investigator's decision that a change of therapy (including immediate HSCT) is in the subject's best interest
- Administration of relevant non-permitted concomitant medications (as outlined in [Section 6.9](#))
- Investigator's decision that a subject does not benefit from treatment anymore, eg, non-response or development of progressive disease
- Intercurrent medical condition, which in the opinion of the investigator or the subject precludes further treatment of the subject
- Withdrawal of subject's consent to further study treatment

All reasons for treatment discontinuation will be documented in the eCRFs. If a subject fails to keep the appointments for study visits, the investigator will document the reason and circumstances as completely and accurately as possible.

In case of premature treatment discontinuation, the assessments planned for end of treatment (end of infusion) should be performed immediately. Exceptions: The CSF examination/prophylaxis does not have to be done in case of premature treatment discontinuation. Bone marrow aspiration/biopsy is not required in case of documented progressive disease. In addition, the SFU visit should be performed 30 days (± 3 days) after the last dose of blinatumomab was administered or, if applicable, before the start of non-protocol-specified therapy or alloHSCT, whichever occurs first. The subject should continue to come to all relevant long-term follow-up visits.

6.7 Hepatotoxicity Stopping and Rechallenge Rules

Subjects with abnormal hepatic laboratory values (ie, ALP, AST, ALT, TBL), and/or international normalized ratio (INR), and/or signs/symptoms of hepatitis (as described below) may meet the criteria for withholding or permanent discontinuation of blinatumomab or other protocol-required therapies as specified in the guidance for industry Drug-Induced Liver Injury (DILI): Premarketing Clinical Evaluation, July 2009.

6.7.1 Criteria for Permanent Discontinuation of Blinatumomab and Other Protocol-required Therapies due to Potential Hepatotoxicity

Blinatumomab and other protocol-required therapies should be discontinued permanently and the subject should be followed according to the recommendations in [Appendix A](#) (Additional Safety Assessment Information) for possible DILI, if ALL of the criteria below are met:

- TBL > 2 x ULN or INR > 1.5
- AND increased AST or ALT from the relevant baseline value as specified below:

Baseline AST or ALT value	AST or ALT elevation
< ULN	> 3x ULN

- AND no other cause for the combination of the above laboratory abnormalities is immediately apparent; important alternative causes for elevated AST/ALT and/or TBL values include, but are not limited to:
 - Hepatobiliary tract disease
 - Viral hepatitis (eg, Hepatitis A/B/C/D/E, Epstein-Barr Virus, cytomegalovirus (CMV), Herpes Simplex Virus, Varicella, toxoplasmosis, and Parvovirus)
 - Right sided heart failure, hypotension or any cause of hypoxia to the liver causing ischemia
 - Exposure to hepatotoxic agents/drugs or hepatotoxins, including herbal and dietary supplements, plants and mushrooms
 - Heritable disorders causing impaired glucuronidation (eg, Gilbert's Syndrome, Crigler-Najjar syndrome) and drugs that inhibit bilirubin glucuronidation (eg, indinavir, atazanavir)
 - Alpha-one antitrypsin deficiency
 - Alcoholic hepatitis
 - Autoimmune hepatitis
 - Wilson's disease and hemochromatosis
 - Nonalcoholic Fatty Liver Disease including Steatohepatitis (NASH)
 - Non-hepatic causes (eg, rhabdomyolysis, hemolysis)
 - Cytokine release syndrome

Approved

If an alternative cause for hepatotoxicity is identified or less stringent conditions developed than what are noted above, determine (based on patient population and/or severity of the hepatotoxicity or event) if blinatumomab and other protocol-required therapies should be withheld or permanently discontinued, as deemed appropriate for the safety of the subject.

6.7.2 Criteria for Conditional Withholding of Blinatumomab and Other Protocol-required Therapies due to Potential Hepatotoxicity

For subjects who do not meet the criteria for permanent discontinuation of blinatumomab outlined above and have no underlying liver disease, and eligibility criteria concerning transaminases and TBL at baseline or subjects with underlying liver disease and baseline abnormal transaminases, the following rules described above in [Table 8](#) for withholding of blinatumomab and other protocol-required therapies.

Blinatumomab and other protocol-required therapies, as appropriate should be withheld pending investigation into alternative causes of DILI. If investigational product(s) is withheld, the subject is to be followed according to recommendations in [Appendix A](#) for possible DILI. Rechallenge may be considered if an alternative cause for impaired liver tests (ALT, AST, ALP) and/or elevated TBL, is discovered and the laboratory abnormalities resolve to normal or baseline ([Section 6.7.3](#)).

6.7.3 Criteria for Rechallenge of Blinatumomab and Other Protocol-required Therapies After Potential Hepatotoxicity

The decision to rechallenge the subject should be discussed and agreed upon unanimously by the subject, investigator, and Amgen.

If signs or symptoms recur with rechallenge, then blinatumomab and other protocol-required therapies, as appropriate, should be permanently discontinued.

Subjects who clearly meet the criteria for permanent discontinuation (as described in [Section 8](#)) should never be rechallenged.

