6.2.2 Dosage, Administration, and Schedule

Blinatumomab is administered as a CIVI.

A single cycle of blinatumomab treatment is 6 weeks in duration, which includes 4 weeks of blinatumomab CIVI followed by a 2 week treatment-free interval. The treatment-free interval may be prolonged by up to 7 days, if deemed necessary by the investigator.

In the first induction cycle, the initial dose of blinatumomab will be 9 µg/day for the first 7 days of treatment (to mitigate for potential cytokine release syndrome [CRS] and CNS events associated with introduction to blinatumomab) which then will be escalated (dose step) to 28 µg/day starting on day 8 (week 2) through day 29 (week 4). For all subsequent cycles (beginning with the second induction cycle and continuing through consolidation, for applicable subjects) 28 µg/day will be the dose for all 4 weeks of continuous treatment.

The drug administration should not be interrupted, if possible. In case of infusion interruption, due to any technical or logistic reason, the interruption should be as short as possible and the infusion continued at the earliest time possible. Every interruption longer than 1 hour should be documented. If the interruption is longer than 4 hours, restart of the infusion should be performed in the hospital, under the supervision of the investigator. The subject should be observed overnight for possible side effects after the restart, either in the hospital or in the outpatient setting as applicable. Administration of dexamethasone premedication as described in [Table 8](#). It is recommended, if possible, that the infusion duration before and after an interruption should total 28 days per treatment cycle.

The daily blinatumomab dose may be up to 10% lower or higher in order to account for possible pump inaccuracies. For dose modifications in case of adverse events see [Section 6.5](#).

A dose of up to 10% higher than the intended dose may not require specific intervention. In case of overdose or medication error, the infusion should be immediately stopped. Routine supportive and symptomatic care according to standard medical practice is recommended. Once the subject is stabilized and no clinically relevant safety findings due to blinatumomab are observed, resumption of blinatumomab at a correct dose can be considered after consultation with the Amgen medical monitor.

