Elevated liver enzymes	Not applicable	
 Interrupt blinatumomab (refer to Section 6.7.2) if any one of the following occurs: 
 TBL > 3 x ULN at any time ALP > 8 x ULN at any time AST or ALT > 8 x ULN at any time AST or ALT > 5 x ULN but < 8 x ULN for ≥ 2 weeks AST or ALT > 3 x ULN with clinical signs or symptoms that are consistent with hepatitis (eg, RUQ abdominal pain/tenderness, fever, nausea, vomiting, jaundice) Permanently discontinue blinatumomab if: 
 TBL > 2 x ULN OR INR > 1.5 (for subjects not on anticoagulant therapy) 
AND
 
 AST or ALT > 3 x ULN (when baseline was < ULN) 
AND
 
 No other cause for the combination of the above laboratory abnormalities is immediately apparent 
Refer to Section 6.7 for additional details

Approved

Footnotes provided on the last page of table

Table 8. Instructions for Treatment Interruption, Dose Modification and Restart

Toxicity	Grade	Instructions for Treatment Interruption and Restart
Other clinically relevant related adverse events ^b	3	
 • Interrupt blinatumomab • Restart blinatumomab at 9 µg/day once improved to grade ≤ 1 or to baseline (refer to Table 7) • Dose step to 28 µg/day after 7 days if toxicity does not recur • Permanently discontinue if: 
 – Initial grade 3 event does not improve to grade ≤ 1 or baseline within 14 days, OR – Grade 3 event reoccurs at the lower dose level within 7 days or reinitiation, OR – Grade 3 event reoccurs at a dose of 9 µg/day without prior step-dose escalation
	4	
 • Permanently discontinue blinatumomab

Page 3 of 3

ALP = alkaline phosphatase; ALT = alanine aminotransferase; AST = aspartate aminotransferase; CRS = cytokine release syndrome; INR = international normalized ratio; RUQ = right upper quadrant; TBL = total bilirubin; ULN = upper limit of normal

Grade scale is based on Common Terminology Criteria for Adverse Events (CTCAE) version 4.03.

^a Obtain brain Magnetic Resonance Imaging (MRI) and perform cerebrospinal fluid (CSF) analysis, if there are no contraindications.

^b For grade 3 or 4 laboratory abnormalities, investigator assessment should be used to determine risk:benefit for each individual patient to continue, interrupt or discontinue blinatumomab treatment.

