7.4.1.2 During Infusion (D1 to D28)

The infusion continues for 28 days, all protocol-required procedures and tests as per [Table 9](#) will be performed on D1 to D15 of each treatment cycle. In addition, the obligatory medication ([Section 6.3](#)) will be given. Replacement of infusion bags will be

performed as described in the IPIM. For the visits on D8, D15 there is a visit window of ± 1 day. Time window for all BM assessments is + 3 days during treatment phase.

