Appendix A. Additional Safety Assessment Information

Adverse Event Grading Scale

Refer to the NCI Common Terminology Criteria for Adverse Events (CTCAE) version 4.03 for adverse event grading and information. The CTCAE scale is available at the following location:

http://ctep.cancer.gov/protocolDevelopment/electronic_applications/ctc.htm

Drug-induced Liver Injury Reporting & Additional Assessments Reporting

To facilitate appropriate monitoring for signals of drug-induced liver injury (DILI), cases of concurrent AST or ALT and TBL and/or INR elevation according to the criteria specified in [Section 6.5](#) require the following:

The event is to be reported to Amgen as a serious adverse event within 24 hours of discovery or notification of the event (ie, before additional etiologic investigations have been concluded).

The appropriate CRF (eg, Adverse Event CRF) that captures information necessary to facilitate the evaluation of treatment-emergent liver abnormalities is to be completed and sent to the Amgen.

Other events of hepatotoxicity and potential DILI are to be reported as serious adverse events if they meet the criteria for a serious adverse event defined in [Section 9.1.3](#).

Approved

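### INR is one of two routes into the permanent liver-injury stop, but after day 2 of each cycle no INR is scheduled through day 29 and none is triggered by rising transaminases

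*Protocol*

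**What the plan says.** Protocol section 6.7.1 sets three conditions for permanent discontinuation, all of which must hold:

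- bilirubin or INR is raised: "TBL > 2 x ULN or INR > 1.5";
- AST or ALT is above 3 x ULN in a subject whose baseline was below ULN;
- no other cause is immediately apparent.

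Table 8 (section 6.5) repeats the rule and limits the INR criterion to subjects not on anticoagulants.

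Table 11 (section 7.2.15) places INR in the coagulation panel, separate from chemistry. Table 9 (section 7.1) sets the visits for each panel. Section 7.4.1.2 says "The infusion continues for 28 days". In cycle 1, section 6.2.2 gives 9 µg/day for the first 7 days and then 28 µg/day "starting on day 8 (week 2) through day 29 (week 4").

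Other liver safeguards do not need an INR:

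- Table 8 requires interruption at several thresholds, including "AST or ALT > 3 x ULN with clinical signs or symptoms that are consistent with hepatitis".
- Section 6.7.2 says treatment "should be withheld pending investigation into alternative causes of DILI" when the withholding criteria apply.
- The last paragraph of 6.7.1 asks for a severity-based decision when an alternative cause is found or "less stringent conditions developed than what are noted above".
- Table 8 footnote b says: "For grade 3 or 4 laboratory abnormalities, investigator assessment should be used to determine risk:benefit for each individual patient" to continue, interrupt or discontinue.

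**The concern.** A mandatory stop rule works only if its inputs are measured when the rule could be met. AST, ALT and bilirubin are measured through the infusion; INR is not. The protocol could cover this with a test triggered by a transaminase rise, but it does not. Appendix A, where 6.7.1 sends the investigator for follow-up, opens with "To facilitate appropriate monitoring for signals of drug-induced liver injury (DILI), cases of concurrent AST or ALT and TBL and/or INR elevation" and then gives only reporting steps.

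At stake is a subject who satisfies the permanent-stop rule through INR but whose scheduled tests prompt no mandatory action. If no INR is ordered, the decision to continue is treated as discretionary when the plan's own rule makes it mandatory. The duty in section 9.2.2.4 to report concurrent transaminase and INR elevation as a serious adverse event also depends on someone having an INR result.

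**Working it through.** The plan states no figure to reproduce here. The check compares the rule with the schedule.

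**1. Scheduled draws.** Table 9 columns are Screening, D1, D2, D3, D8, D15, D29, safety follow-up (SFU) and long-term follow-up.

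| Panel | Scr | D1 | D2 | D3 | D8 | D15 | D29 | SFU |
|---|---|---|---|---|---|---|---|---|
| Chemistry (AST, ALT, bilirubin) | X | X | X | | X | X | X | X |
| Coagulation (INR) | | X | X | | | | | X |

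The table was read by machine, so the column mapping was tested on rows whose visits are also stated in footnotes. Urinalysis decodes to D1 and SFU, as in Table 11 footnote a. Lymphocyte subsets decode to D1, D2, D29 and SFU, as in Table 9 footnote f. The blanks in the coagulation row therefore do not look like an extraction fault.

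**2. Length of the gap.** An INR is drawn on D2 itself, so the gap starts after that draw.

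- D2 to D29: 29 − 2 = 27 days, within a 28-day infusion.
- Of the five in-cycle chemistry draws (D1, D2, D8, D15, D29), three have no paired INR (D8, D15, D29).
- Next scheduled INR if another cycle follows: D43, which is 43 − 2 = 41 days after D2.
- Next scheduled INR if a completed cycle is the last: SFU at about D59 (29 + 30), which is 57 ± 3 days after D2.

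**3. Dose covered by the gap in cycle 1.**

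- Planned: 7 x 9 + 21 x 28 = 651 µg, as in SAP section 6.
- After D2: 6 x 9 + 21 x 28 = 642 µg, and 642/651 = 98.6%.
- First scheduled INR during a 28 µg/day infusion: D2 of cycle 2, study day 43 + 1 = 44, or day 51 if the treatment-free interval is extended by 7 days. This assumes no interruption or restarted cycle.

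**4. Search for a triggered INR.** Sections 6.5, 6.7.1 to 6.7.3 and 9.2.2.4 and Appendix A use INR as a criterion or for reporting, or do not mention it. None orders the test. Early discontinuation under section 6.6 calls for the end-of-infusion assessments, which contain no coagulation panel. Section 7.9 allows safety tests on collected blood but requires none. SAP section 10.6.2 summarises potential Hy's Law cases and adds no test.

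**5. What remains uncovered.** Removing everything another rule catches leaves a subject with all of the following:

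- baseline AST/ALT below ULN;
- on-treatment AST/ALT above 3 x ULN but below the Table 8 interruption limits, and without hepatitis signs;
- bilirubin not above 2 x ULN;
- INR above 1.5, not on anticoagulants;
- no other apparent cause;
- no INR ordered at the investigator's discretion.

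AST/ALT above 3 and up to 5 x ULN is grade 2 (SAP Appendix B, Table 2), so the grade 3 row of Table 8 does not reach it. Between 5 and 8 x ULN for less than 2 weeks, footnote b leaves the decision to the investigator.

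**The case against.** The strongest reply is that Table 9 is a minimum and the rule is built around clinical work-up. Excluding other causes already needs tests that Table 9 does not list, such as viral and autoimmune work-up, and section 9.2.2.4 expects further etiologic investigation. An investigator applying a rule that names INR has good reason to order one. This stands in part: an unscheduled INR fits the design, and the schedule does not contradict the rule. But leaving the test to initiative is weaker than requiring it, and INR is what tells the investigator whether the mandatory or the discretionary provision applies.

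The reply is also right that other provisions shrink the group. The symptom limb of Table 8 includes fever, nausea and vomiting, which are common in this population. The list of alternative causes includes cytokine release syndrome, infection and hepatotoxic drugs. Exclusion 226 admits subjects with AST/ALT up to just under 5 x ULN, and those with a baseline at or above ULN fall outside this rule altogether.

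A reader might infer from the 27 days or the 98.6% of dose that subjects lack liver protection for almost the whole infusion. The documents do not support that. Those figures measure time and dose since the last scheduled INR. The bilirubin route has data on D8, D15 and D29, and the interruption and withholding rules operate throughout. A reader might also infer that the 24-hour reporting deadline would be breached. It would not, because that clock starts at discovery or notification.

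**Conclusion.** The point holds in a limited form. After the D2 draw of each cycle, one of two stated routes into a mandatory permanent stop has no scheduled or triggered input through D29. A site following the protocol exactly could therefore keep a subject on infusion who meets the stop rule.

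The group is narrow. The documents give no frequency, and it is probably low. The thresholds are not in question, and the primary endpoint is not affected. It would go too far to say that the hepatotoxicity rules are inoperative or that subjects are unmonitored. The conclusion rests on the column reading of Table 9, which two footnoted rows support, and on finding no instruction in the protocol or SAP to obtain an INR when transaminases rise. This is a cheap safety improvement, not a flaw in the trial's inference.

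**What to change.** Add one sentence to section 6.7.1 and to the liver row of Table 8: when AST or ALT exceeds 3 x ULN on treatment in a subject whose baseline was below ULN and who is not on anticoagulants, a local INR must be obtained promptly, on the same day where possible. The baseline condition keeps the test to subjects in whom the result could activate the rule. The anticoagulant condition follows Table 8.

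Coagulation is already run locally (section 7.2.15), so no visit or central sample is needed. The documents do not give the share of subjects with AST/ALT above 3 x ULN. Assuming 10% to 40% of 120 subjects with 1 to 3 tests each, the cost is 120 x 0.10 x 1 = 12 to 120 x 0.40 x 3 = 144 tests, and less where the share includes subjects whom the two conditions remove.

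Routine INR on D8, D15 and D29 is not needed. It would add up to 120 x 2 x 3 = 720 tests if every subject had 2 cycles and 120 x 5 x 3 = 1,800 if every subject had 5.

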4.1.2 Exclusion Criteria

Disease Related

- 201 Subjects with Ph-positive ALL
- 202 Subjects with Burkitt's Leukemia according to World Health Organization (WHO) classification
- 203 History or presence of clinically relevant CNS pathology as epilepsy, seizure, paresis, aphasia, stroke, severe brain injuries, dementia, Parkinson's disease, cerebellar disease, organic brain syndrome, and psychosis
- 204 Active ALL in the CNS (confirmed by cerebrospinal fluid [CSF] analysis) or in testes
- 205 Isolated extramedullary disease
- 206 Current active autoimmune disease or history of autoimmune disease with potential CNS involvement

Other Medical Conditions

- 207 History of malignancy other than ALL within 5 years prior to start of protocol-specified therapy with the exception of:
 - Malignancy treated with curative intent and with no known active disease present for 5 years before enrollment and felt to be at low risk for recurrence by the treating physician
 - Adequately treated non-melanoma skin cancer or lentigo maligna without evidence of disease
 - Adequately treated cervical carcinoma in situ without evidence of disease
 - Adequately treated breast ductal carcinoma in situ without evidence of disease
 - Prostatic intraepithelial neoplasia without evidence of prostate cancer.
- 208 Known infection with human immunodeficiency virus (HIV) or chronic infection with hepatitis B virus (HBsAg positive) or hepatitis C virus (anti-HCV positive)
- 226 Abnormal screening laboratory values as defined below:
 - Aspartate aminotransferase (AST) and/or alanine aminotransferase ALT and/or ALP ≥ 5 x upper limit of normal (ULN)
 - Total bilirubin (TBL) ≥ 1.5 x ULN (unless related to Gilbert's or Meulengracht disease)
 - Creatinine ≥ 1.5 ULN and creatinine clearance < 60 ml/min (calculated)

Approved

Medications or Other Treatments

- 210 Autologous HSCT within 6 weeks prior to start of blinatumomab treatment
- 211 AlloHSCT within 3 months prior to start of blinatumomab treatment
- 212 Any active acute Graft-versus-Host Disease (GvHD), grade 2-4 according to the Glucksberg criteria or active chronic GvHD requiring systemic treatment
- 213 Any systemic therapy against active GvHD within 2 weeks prior to start of blinatumomab treatment

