- 214 Cancer chemotherapy within 2 weeks prior to start of blinatumomab treatment (intrathecal chemotherapy and dexamethasone are allowed until start of blinatumomab treatment). In addition, any subject whose organ toxicity (excluding hematologic) from prior ALL treatment has not resolved to common terminology criteria for adverse events (CTCAE) \leq grade 1.
- 215 Radiotherapy within 2 weeks prior to start of blinatumomab treatment
- 216 Immunotherapy (eg, rituximab) within 4 weeks prior to start of blinatumomab treatment
- 217 Currently receiving treatment in another investigational device or drug study, or less than 4 weeks prior to start of blinatumomab treatment.
- 218 Previous treatment with anti-CD19 therapy

General

- 219 Known hypersensitivity to immunoglobulins or to any other component of the IMP formulation
- 220 Pregnant women and women planning to become pregnant should not participate in this study. Subjects who are breast feeding prior to start of blinatumomab treatment may be enrolled if they stop breast feeding with breast milk produced during blinatumomab treatment and for an additional 48 hours after the last dose of blinatumomab
- 222 Male participants are not required to use birth control during treatment with blinatumomab. However, you should let your female partner know you are in this study.
- 223 Subject likely to not be available to complete all protocol-required study visits or procedures, including follow-up visits, and/or to comply with all required study procedures to the best of the subject and investigator's knowledge.
- 224 History or evidence of any other clinically significant disorder, condition or disease (with the exception of those outlined above) that, in the opinion of the Investigator or Amgen physician, if consulted, would pose a risk to subject safety or interfere with the study evaluation, procedures or completion.
- 225 Previous treatment with blinatumomab
- 227 Woman of childbearing potential and is not willing to use an effective method of contraception during treatment and for an additional 48 hours after the last dose of blinatumomab. Birth control is not required for postmenopausal women, or women with uterus/or both ovaries/ or both fallopian tubes removed.

Approved

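### The combined liver stop has no criterion when AST and ALT are both at or above ULN at baseline, which leaves a narrow band with no required interruption and no clear 24-hour DILI report

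*Protocol*

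**What the plan says.** **The stop.** Section 6.7.1 of the protocol makes discontinuation permanent only if every listed criterion is met. One criterion reads "AND increased AST or ALT from the relevant baseline value as specified below". The table beneath it has a single row, for baseline AST or ALT below ULN. Table 8 in section 6.5 carries the same limit: "AST or ALT > 3 x ULN (when baseline was < ULN)". The missing row is therefore in the plan and not a fault of text extraction.

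**Who can enrol.** Exclusion 226 removes subjects only at AST, ALT or ALP of 5 x ULN or more. For bilirubin it excludes "Total bilirubin (TBL) ≥ 1.5 x ULN", apart from Gilbert's or Meulengracht disease. Section 6.7.2 expressly foresees subjects with abnormal transaminases at baseline.

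**Interruption lines.** At any baseline, Table 8 interrupts for bilirubin > 3 x ULN, ALP > 8 x ULN, AST/ALT > 8 x ULN, "AST or ALT > 5 x ULN but < 8 x ULN for ≥ 2 weeks", or "AST or ALT > 3 x ULN with clinical signs or symptoms that are consistent with hepatitis".

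**Reporting.** Section 9.2.2.4 requires a 24-hour report for concurrent AST/ALT and bilirubin or INR elevation that meets the criteria in section 6.7. Appendix A uses the same text but points to section 6.5. Other hepatotoxicity is reported only if it meets the ordinary SAE criteria.

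**The concern.** The plan treats raised transaminases together with raised bilirubin or INR, unexplained, as serious enough for a mandatory permanent stop and a prompt report. It defines that combination only for subjects whose transaminases were normal at entry. A subject who enters slightly above ULN and then reaches the same on-treatment values has no matching rule.

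The bilirubin component is unlikely to be carried over from baseline. Entry bilirubin is below 1.5 x ULN (with the exception above), so passing 2 x ULN is a rise of more than 2/1.5 - 1 = 33%.

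At stake is continued infusion, and a delayed report, in a possible drug-induced liver injury. The text also does not say which baseline counts when only one of the two enzymes was raised at entry.

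**Working it through.** The plan states no figure to reproduce. The check is a trace of the rules as written.

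**Notation** (all x ULN except INR): b = baseline of both enzymes, x = on-treatment AST or ALT, T = bilirubin, P = ALP.

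**Permanent stop** (6.7.1, Table 8): (T > 2 or INR > 1.5) and (b < 1 and x > 3) and no other apparent cause. The condition b < 1 is required, so the stop is false for every b of 1 or more.

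**Liver interruption lines** (Table 8):
- L1: T > 3
- L2: P > 8
- L3: x > 8
- L4: 5 < x < 8 for at least 2 weeks
- L5: x > 3 with hepatitis signs or symptoms

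**Cases** (no other cause, P not raised, no anticoagulants):

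| Case | x | T | INR | Symptoms | b = 0.9 | b = 1.2 |
|---|---|---|---|---|---|---|
| A | 4.5 | 2.8 | normal | no | stop and report | L1 to L5 all false |
| B | 7 | 2.8 | normal | no | stop and report | no liver line until L4 at 2 weeks |
| C | 4.5 | 1.4 | 1.8 | no | stop and report | L1 to L5 all false; none uses INR |
| D | 9 | 3.5 | normal | no | stop and report | L1 and L3: interruption; report arguably applies |
| E | 4.5 | 2.8 | normal | yes | stop and report | L5: interruption |

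**Grade 3 row.** Table 8 also has a row for other clinically relevant related adverse events, which interrupts at grade 3. By the laboratory limits in SAP Appendix B, Table 2, grade 2 is AST/ALT > 3 to 5 and bilirubin > 1.5 to 3 x ULN; grade 3 AST/ALT is > 5 to 20 x ULN.
- Case A is grade 2 on both values, so this row does not reach it.
- Case B has grade 3 AST/ALT, so the row may apply if the event is judged related and clinically relevant. Footnote b then says that "investigator assessment should be used to determine risk:benefit for each individual patient to continue, interrupt or discontinue blinatumomab treatment".

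**The resulting gap.**
- Clear gap, at any duration: x > 3 to 5, with T > 2 to 3 or with INR > 1.5 and T at most 3; P at most 8; no hepatitis signs or symptoms; no other apparent cause.
- Partial gap: x > 5 to 8 for under 2 weeks. No liver line fires, but the grade 3 row may. At exactly x = 8 neither L3 nor L4 is true, whatever the duration.

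**Grid check.** The rules were evaluated at b = 1, 2, 4.9; x = 3.1, 4, 5, 5.1, 6, 7.9, 8; six bilirubin/INR pairs with T at most 3 that meet T > 2 or INR > 1.5; 0 to 3 weeks; P = 1, 8, 8.1; no symptoms. That is 3 x 7 x 6 x 4 x 3 = 1,512 points. The stop was met at none of them. With x at most 5 and P at most 8 (3 x 3 x 6 x 4 x 2 = 432 points), no interruption line fired. These are counts of rule combinations, not probabilities.

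**Timing** (Table 9). Chemistry is scheduled on D1, D2, D8, D15, D29 and at safety follow-up.
- First above 5 x ULN on D8 or D15: scheduled samples show 2 weeks only at D29, the end of infusion (21 and 14 days later).
- First seen on D2: 13 days old at D15, or 14 with the +1 day window.
- Unscheduled tests could show it earlier.
- Coagulation is scheduled on D1 (before infusion), D2 and safety follow-up, so the INR route has one scheduled on-infusion sample per cycle.

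**The case against.** The strongest defence is that the sponsor did consider these subjects and left them to withholding rules and judgement.

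- Section 6.7.2 names abnormal-baseline subjects and says treatment should, as appropriate, be withheld while other causes of liver injury are investigated. That sentence follows a pointer to Table 8, so whether it adds a duty where no Table 8 line is met is arguable.
- Section 6.7.1 asks for a case-by-case decision in milder situations, and 6.6 allows discontinuation for an adverse event at the investigator's discretion.
- Section 6.7 opens by citing an industry DILI guidance, which could be read as widening its criteria. A potential case can also go in within 24 hours as an SAE under the medically important criterion.
- SAP 10.6.2 summarises potential Hy's Law cases.
- The band is narrow in practice. Fever or nausea consistent with hepatitis removes a subject from it. Cytokine release syndrome and hepatotoxic drugs count as other causes. Exclusion 214 also removes "any subject whose organ toxicity (excluding hematologic) from prior ALL treatment has not resolved to common terminology criteria for adverse events (CTCAE") grade 1 or better.

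Much of this stands, and it limits the point. It does not close the gap. Grade 1 AST/ALT runs to 3 x ULN in the SAP table, so exclusion 214 still admits a baseline of 1.2 x ULN. The Hy's Law summary is a tabulation, not a prompt report. The other provisions rest on judgement where the plan fixes a mandatory stop for a normal baseline.

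A reader might infer that subjects with raised baseline enzymes have no liver protection, or that nothing applies up to 8 x ULN. The documents do not support either: five interruption lines apply at any baseline, the 2-week line and possibly the grade 3 row reach values above 5 x ULN, and any hepatitis sign or symptom empties the band.

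**Conclusion.** The point stands in a limited form. When both AST and ALT are at or above ULN at baseline, the combined stop cannot be met as worded. For AST/ALT > 3 to 5 x ULN under the conditions set out above, no Table 8 line fires and only discretion remains. For > 5 to 8 x ULN lasting under 2 weeks, no liver line fires, but the grade 3 row may. The INR route is real on paper but will seldom show on scheduled samples.

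On reporting, the supportable statement is that the 24-hour DILI report is not clearly triggered. It would go too far to say that the plan rules it out, given the guidance reference and the SAE route.

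This rests on a literal reading of 6.7.1 and Table 8, and on the SAP laboratory limits for grade; the investigator's event grade may differ. The documents give no distribution of baseline enzymes, so the number of subjects affected cannot be derived. It is a specific safety-rule gap with a small correction, and worth making.

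**What to change.** 1. **Report.** Make the 24-hour DILI report in 9.2.2.4 and Appendix A apply at any baseline when AST or ALT is > 3 x ULN and has risen from its own baseline, with bilirubin > 2 x ULN or INR > 1.5 (not on anticoagulants) and no other cause immediately apparent. Point both sections to the same criteria.
2. **Withholding.** Add a row for baseline at or above ULN to the 6.7.1 table and to Table 8, requiring at least withholding pending investigation under 6.7.2. It should need a meaningful rise over that enzyme's own baseline. The documents give no multiple, so the sponsor must set one. Any rise at all would be too loose: 4.5 to 4.6 x ULN with INR > 1.5 would qualify.
3. **Baseline.** State that each enzyme is judged against its own baseline.

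The cost is wording in two tables and two reporting sections; chemistry is already scheduled. The downside is a few more reports and interruptions, number not derivable. Some interruptions may become permanent, because 6.7.2 allows rechallenge only if an alternative cause is found and the values resolve, and 6.6 ends treatment after an interruption of more than 2 weeks for a related event (up to 7 more days for logistics). The sponsor should weigh that when choosing the multiple.
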